2.0 CLINICAL BACKGROUND

Aortic valve stenosis (AS) is a common condition in which the aortic heart valve thickens and calcifies, preventing it from opening fully. This dysfunction limits blood flow from the heart to the rest of the body and leads to significant left ventricular hypertrophy. Untreated AS leads to heart failure, syncope, stroke, sudden cardiac arrest, and premature death. Treatment requires mechanical replacement of the diseased valve as there is no medical therapy.

Treatment of severe AS has traditionally been performed by cardiac surgeons with surgical aortic valve replacement (SAVR). This open-heart surgery requires complete cardiac arrest and cardiopulmonary bypass. Because of the magnitude of the procedure, higher risk patients with aortic stenosis are frequently not candidates for SAVR.

Transcatheter aortic valve replacement (TAVR), a minimally invasive procedure that uses catheter-based systems to percutaneously deliver self-expanding and balloon-expanding heart valves, was approved by the FDA in 2011. While this minimally invasive approach has revolutionized treatment methods for high-risk surgical patients who have aortic valve stenosis, there are risks associated with the use of large-bore catheters in the cardiovascular system. Even with recent technological advances, periprocedural stroke remains a devastating complication that significantly impacts mortality (Shimamura). This risk has been of increased concern since 2016, when TAVR was expanded to include intermediate risk patients. The average age of patients undergoing the TAVR procedure was found in a meta-analysis of 31 studies to be 81.5 years with a standard deviation of 7.0 years (Chakos), while the average age of patients undergoing the TAVR procedure in the large PARTNER trial was 84.0 years with a standard deviation.

During the TAVR procedure, cerebral emboli have been shown to originate from atheromatous plaques within the aorta and from the degenerate stenotic aortic valve itself. An analysis on 3,687 subjects from the CoreValve (Medtronic) U.S. Extreme Risk and High Risk Pivotal Trials and Continued Access Registry reported a stroke rate of 4.1% in the first 10 days post-TAVR (Kleiman). The PARTNER trial, which evaluated the Sapien device (Edwards Lifesciences) in 2,621 subjects, reported cerebrovascular events in 3.8% at 30 days (Kapadia). This data illustrates the clinical need for embolic protection, which may have a significant role to play in the continued safety and adoption of TAVR as a treatment, especially for the intermediate risk patient population for which TAVR is currently being offered.

Several embolic protection devices are in different stages of investigation in the U.S. PROTECTED TAVR is a landmark randomized control clinical trial currently underway comparing non-embolic protected TAVR to embolic protected TAVR using the Sentinel device (Boston Scientific, Inc.), which is the only embolic protection device currently cleared by FDA.

The embolic protection products that are currently approved or under investigation are standalone from the TAVR systems that require separate procedures with separate anatomical access points, thus increasing the complexity and risk. The investigational device is intended to provide a transformative development in the safety and ease of use of embolic protection products by providing full cerebral protection using a technology platform that is integrated into the normal workflow of the TAVR procedure.

3.0 TREATMENT DESCRIPTION

3.1 Device Description

The EmStop Embolic Protection System (EmStop System) is a catheter-based filter system that captures and removes debris dislodged during transcatheter aortic valve replacement (TAVR) procedures. The EmStop System is composed of a preloaded introducer sheath, delivery catheter, and filter sheath (**Figure 1**), as described below. Refer to **Table 1** for system specifications.

• Figure 1: EmStop Embolic Protection System

3.1.1 Introducer sheath

The introducer sheath is a single lumen, braid-reinforced catheter used to gain access to the vasculature and to facilitate placement and removal of the filter sheath and delivery catheter (**Figure 2**). The proximal end of the introducer sheath comprises a hub with Tuohy Borst cap and a one-way stopcock for flushing.

3.1.2 Delivery catheter

A single lumen, braid-reinforced catheter that facilitates delivery of the filter sheath into the aortic arch and controls deployment of the filter via internal actuation wires and a thumb slider

interface on the proximal handle (**Figure 3**). The distal end of the delivery catheter handle contains release clips for connection with the filter sheath. The delivery catheter has a radiopaque distal tip and a nonradiopaque (yellow) marking on the shaft to identify the shaft outside diameter (OD) transition; the force required to remove the device changes at this transition. A Luer connector on the proximal end of the handle is used for flushing.

3.1.3 Filter sheath

The filter sheath is a single lumen, braid reinforced catheter with a distal filter (**Figure 4**). This sheath provides a central lumen that allows for passage of TAVR devices. The proximal hub contains a hemostasis valve to allow for connection with the delivery catheter and passage of the TAVR system. The one-way stopcock allows for filter sheath flushing. The filter sheath shaft has a blue depth marker to indicate when the filter has been "sheathed" and a yellow depth marker to indicate an approximate 1" zone (at the transition between the filter and the shaft) where higher resistance is expected during sheath removal.

The distal end of the filter sheath has an attached filter, which is retained in a low-profile delivery state by the actuation wires. During deployment of the filter sheath, the actuation wires are operated via the thumb slider on the delivery catheter handle. The filter is composed of an exterior self-expanding nitinol braid and an interior attached nylon mesh (**Figure 5**).

Figure 5: EmStop Filter

Table 1: EmStop Embolic Protection System Specifications

Aorta size compatibility	25 - 40 mm
TAVR delivery system compatibility	 Abbott FlexNav Delivery System (14F equivalent, 6.00 mm capsule outer diameter)
	 Medtronic CoreValve EnVeo PRO Delivery System (14F equivalent, 6.00 mm capsule outer diameter)
	 Medtronic CoreValve Evolut PRO+ Delivery System (14F equivalent, 6.00 mm capsule outer diameter)
Working length (delivery catheter & filter sheath)	90.17 cm (35.5 in)
Guidewire compatibility	0.035", 260 cm, high support
Introducer sheath size	21F
Introducer sheath working length	43.5 cm
Delivery catheter	18F OD, 0.035" ID
Filter sheath ID	18.5F
Filter pore size	140 μm

The device is provided to users in its delivery state, as shown in **Figure 1** above. A packaging mandrel is placed in the distal tip and the system is packaged on a backer card, sealed within a single sterile barrier Tyvek pouch, and placed into a shelf box. The EmStop Embolic Protection System is sterilized by ethylene oxide (EtO).

3.1.4 Device Manufacturer

The EmStop System is manufactured for the study sponsor by Resolution Medical (Fridley, MN, USA).

3.1.5 Device Labeling / Instructions for Use

The device instructions for use will be included with the investigational product.

3.2 Principle of Operation / Mechanism of Action

The EmStop System provides embolic protection during TAVR procedures while preserving virtually the same sequence and number of steps as unprotected TAVR. The EmStop System contains a central lumen for TAVR device insertion, which eliminates the need for a concomitant vascular entrance point.

After femoral access is obtained and the guidewire is advanced to the targeted location, the EmStop System is loaded onto the guidewire and advanced to the targeted location. Next, the filter sheath is advanced under fluoro guidance, and the filter is deployed in the target location within the ascending aorta (i.e., between the innominate takeoff and the aortic valve; the specific location may vary from patient to patient). The TAVR device is inserted through the EmStop System, and the procedure is conducted per the TAVR device IFU. After the TAVR procedure, the EmStop device is withdrawn, and the emboli captured in the filter is removed from the patient.

The EmStop expanded filter provides filtration, collection, and removal of emboli liberated into the proximal aorta during the TAVR procedure. The filter is deployed in the ascending aorta proximal to any branch artery, thus protecting the brain and vital organs from embolic damage. Embolic material may be aspirated through the filter sheath during the TAVR procedure. Upon completion of the TAVR procedure, the filter and the captured embolic material are withdrawn into the sheath and removed from the patient.

3.3 Proposed Indications for Use

The EmStop Embolic Protection System is indicated for use as an embolic protection device to capture and remove thrombus/debris while performing transcatheter aortic valve replacement procedures. The diameters of the aorta at the site of filter placement should be between 25 – 40mm.

4.0 OBJECTIVE

The objective of this study is to demonstrate safety and investigate performance of the EmStop Embolic Protection System when used as indicated.

5.0 ENDPOINTS

5.1 Primary Safety Endpoint

The primary safety endpoint for the study is the occurrence of MACCE at 30 days, defined as a composite of the following VARC-2 defined components:

- All-cause mortality
- All stroke (disabling and non-disabling)
- Acute kidney injury (AKI) Stage 2 or 3 (including renal replacement therapy) within 72 hours

5.2 **Primary Performance Endpoint**

The primary performance endpoint for the study is device procedural success, defined as successful insertion, deployment, positioning, and removal of the EmStop System in the absence of device interference.

5.3 Secondary Endpoints

The following secondary endpoints will be evaluated:

- Gross and histologic evaluation of captured embolic debris, including particle presence, count, size, and composition (assessed by an independent pathology core laboratory)
- Average number of captured particles ≥140 µm in diameter (assessed by an independent pathology core laboratory)
- Total acute infarct burden, as measured by diffusion-weighted imaging (DWI), also referred to as DW-MRI, within 14 days pre-procedure and at 18-36 hours post-procedure (assessed by an independent reader). This outcome will be evaluated and tabulated to include total lesion count, average (mean) lesion volume and median lesion volume.
- Occurrence of Transient Ischemic Attack (TIA)

5.4 Ancillary Measures

Additional ancillary data to be collected and evaluated include:

- Physician usability evaluation of:
 - Device usage
 - Device deployment
 - Device retrieval
 - Filter sheath advancement
 - Delivery catheter removal
 - Filter sheath removal
- Filter retraction
- Use of bail out procedures

5.5 Rationale for Study Endpoints

Study endpoints have been selected to align with the objectives of the trial (safety and performance). In particular, the primary safety endpoint, occurrence of MACCE at 30 days, is the same as used in prior regulated investigations of similar devices, while the primary performance endpoint is defined in a manner to permit evaluation of deployment, usage and retrieval of the EmStop System. Secondary endpoints were then selected to provide additional information on both safety and performance, as listed above.

6.0 STUDY DESIGN

6.1 Overall Design

The investigation is a prospective, multi-center, single arm feasibility study. Subjects will undergo treatment with a currently marketed TAVR device and the EmStop Embolic Protection System and will then be followed to 30 days post-procedure.

This is a treatment-only feasibility investigation intended to capture and characterize outcomes, especially safety outcomes, with the EmStop System. Results from this study will inform the design of larger future studies.

6.2 Number of Sites & Subjects

The study will be conducted in up to 2 investigational sites in the U.S. This study will enroll up to 15 subjects. Each site will enroll a minimum of 5 subjects and a maximum of 10 subjects.

6.3 Study Population

The population for this study is subjects with severe native aortic valve stenosis who meet clinically approved indications for TAVR. The investigation population aligns with the EmStop System proposed indications.

The study will be conducted in adult subjects and does not include any other age, gender, or racial and ethnic origin restrictions. Women who have known pregnancy or who are nursing are excluded because of the risks of radiation exposure that occurs during the TAVR procedure and the medications (e.g., blood thinners) that may be needed.

6.4 Study Duration

Enrollment is expected to take approximately 3 months. Each study subject will actively participate in the study through 30-day follow-up. The overall study duration, from screening the first patient to the final follow-up visit, data analysis, and final report, is expected to be approximately 6-9 months.

6.5 Subject Eligibility Criteria

6.5.1 General Inclusion Criteria

Subjects must meet all the following inclusion criteria:

Clinical inclusion criteria

- 1. Between 21 and 90 years of age at the time of consent
- 2. Meets FDA approved indications for transcatheter aortic valve replacement (TAVR) procedure on a native aortic valve using a commercially available Abbott or Medtronic transcatheter heart valve

- 3. Willing and able to provide written informed consent and written HIPAA authorization prior to initiation of study procedures
- 4. Willing and able to comply with the protocol-specified procedures and assessments

6.5.2 Angiographic Inclusion Criteria (assessed via computed tomography)

- 5. Subject anatomy is compatible with correct device deployment and positioning with:
 - Ability to achieve access with a 21 French equivalent femoral access sheath
 - Ascending aorta length ≥8 cm
 - Ascending aorta/aortic arch diameter is ≥ 25 or ≤40 mm
 - Ascending aorta or aortic arch exhibits ≤ Grade 1 atheromatous disease and limited wall calcification

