Proposed Device Indications for Use	The EmStop Embolic Protection System is indicated for use as an embolic protection device to capture and remove thrombus/debris while performing transcatheter aortic valve replacement procedures. The diameters of the aorta at the site of filter placement should be between 25 – 40 mm.		
Study Design	The investigation is a prospective, multi-center, single arm feasibility study. Subjects will undergo treatment with a currently marketed TAVR device and the EmStop Embolic Protection System and will then be followed to 30 days post- procedure. This is a treatment-only feasibility investigation intended to capture and characterize outcomes, especially safety outcomes, with the EmStop System.		
Number of Sites & Subjects	The study will be conducted in up to 2 investigational sites in the U.S. This study will enroll up to 15 subjects.		
Study Population	The population for this study is subjects with severe native aortic valve stenosis who meet clinically approved indications for TAVR. The investigation population aligns with the EmStop System proposed indications. The study will be conducted in adult subjects and does not include any other age, gender, or racial and ethnic origin restrictions.		
Primary Safety and Performance Endpoints	The primary sa days, defined a Al Al Ad th The primary po defined as suc EmStop Syste	afety endpoint for the study is the occurrence of MACCE at 30 as a composite of the following VARC-2 defined components: I-cause mortality I stroke (disabling and non-disabling) cute kidney injury (AKI) Stage 2 or 3 (including renal replacement erapy) within 72 hours erformance endpoint for the study is device procedural success, ccessful insertion, deployment, positioning, and removal of the m in the absence of device interference.	

EmStop, Inc.		CLINICAL STUDY PROTOCOL SYNOPSIS EmStop Study Number: EMS-CL-5000

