6.5.3 General Exclusion Criteria

Subjects must not meet any of the following exclusion criteria:

- 1. Requires urgent or emergent TAVR procedure
- 2. Contraindicated to MRI
- 3. Previously implanted aortic or mitral valve bioprosthesis
- 4. Hepatic failure (Child-Pugh class C)
- 5. Hypercoagulable state that cannot be corrected by additional periprocedural heparin
- 6. Planned to undergo any other cardiac surgical or interventional procedure (e.g., concurrent coronary revascularization) during the TAVR procedure or within 30 days prior to the TAVR procedure. NOTE: Diagnostic cardiac catheterization is permitted up until baseline MRI is obtained. Once baseline MRI is obtained, no additional intra-aortic or intracardiac procedure may occur.
- 7. Acute myocardial infarction within 30 days of the planned index procedure
- 8. Renal failure, defined as estimated glomerular filtration rate (eGFR) <30 mL/min
- 9. Documented history of stroke or TIA within the prior 6 months, or any prior stroke with a permanent major disability or deficit (NIHSS >1 at baseline)
- 10. Left ventricular ejection fraction ≤30% within 3 months prior to procedure
- 11. History of intolerance, allergic reaction, or contraindication to any of the study medications, including heparin, aspirin, clopidogrel, or a sensitivity to contrast media or anesthesia that cannot be adequately pre-treated
- 12. Known allergy or sensitivity to nickel-titanium
- 13. Active endocarditis or ongoing systemic infection, defined as fever (>38°C) and/or white blood cell (WBC) >15,000 IU

- 14. Undergoing therapeutic thrombolysis
- 15. History of bleeding diathesis or a coagulopathy
- 16. Known or suspected to be pregnant, or is lactating; female subjects of child-bearing potential must have a negative serum or urine pregnancy test within 48 hours prior to the index study procedure.
- 17. Currently participating in another drug or device clinical study
- 18. Any other clinical reason, as deemed by the investigators of the study, by which the patient would not be an appropriate candidate for the study
- 19. Vulnerable subject populations (e.g., incarcerated or cognitively challenged adults)

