7.1 Screening Visit

The study team will screen patients for the study. Screening is defined as the process of reviewing a patient's medical records against the study eligibility criteria to determine if the patient is eligible to enroll in the study. It is expected that the medical records will contain adequate information to determine if a patient meets most of these criteria; this includes the computed tomography (CT) completed as part of the standard of care TAVR screening process. The investigator will visually assess the CT imaging to ensure angiographic inclusion criteria are met.

If the investigator (or designee) determines the patient meets all clinical inclusion and exclusion criteria (except criteria verified by blood or urine testing after consent), they can be consented for study participation, after which all remaining non-angiographic eligibility criteria will be verified prior to the procedure.

Sites will be required to maintain a screen failure log that contains rationale for subjects who became screen failures after consent.

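### The aortic-diameter inclusion bullet joins its two limits with *or*, so as written it excludes no diameter and does not match the 25 to 40 mm range given elsewhere in the protocol

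*Combined protocol and SAP*

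**What the plan says.** Criterion 5 in Section 6.5.2 opens with a general requirement, "Subject anatomy is compatible with correct device deployment and positioning with", followed by four bullets. The third is the diameter rule: "Ascending aorta/aortic arch diameter is ≥ 25 or ≤40 mm". The synopsis joins the same two limits with the same *or*.

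Three other places give an aortic size, and all give a closed range of 25 to 40 mm:

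- the proposed indication in the synopsis: "The diameters of the aorta at the site of filter placement should be between 25 – 40 mm";
- the same indication in Section 3.3;
- the aorta-size row of the device specifications in Table 1.

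Section 6.3 then states: "The investigation population aligns with the EmStop System proposed indications". None of the 19 exclusions in Section 6.5.3 mentions a diameter. The bullet is applied at screening under Section 7.1: "The investigator will visually assess the CT imaging to ensure angiographic inclusion criteria are met".

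**The concern.** An inclusion bullet with two numerical limits is there to keep out subjects below the lower one and above the upper one. Joined by *or*, the limits do neither, so a reader who applies the bullet literally has no diameter restriction at all.

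The range matters because Table 1 presents it as a device-compatibility specification, and the primary performance endpoint (Section 5.2) is successful insertion, deployment, positioning and removal of that device. A subject counts as enrolled once the device has entered the body (Section 7.3). The primary analysis uses all enrolled subjects (Section 8.1), so anyone admitted outside the range would appear in both primary summaries (Sections 8.3 and 8.4).

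The wording also weakens detection. Section 12.8 defines a deviation as a failure to follow the protocol. Measured against this bullet, an out-of-range enrolment would not be a clear deviation.

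**Working it through.** The plan gives no figure to reproduce here. The check is one of logic.

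**Inputs.** Lower limit 25 mm and upper limit 40 mm, both from the bullet in Section 6.5.2 and the synopsis. Comparison range 25 to 40 mm, from the synopsis indication, Section 3.3 and Table 1. Maximum enrolment 15, from Section 6.2.

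**Step 1: the bullet as written.** Let d be the diameter in mm. The condition is d ≥ 25 or d ≤ 40.

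- If d < 25, then d ≤ 40 is true, so d passes.
- If 25 ≤ d ≤ 40, both limits are met, so d passes.
- If d > 40, then d ≥ 25 is true, so d passes.

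These cases cover every d, so nothing is excluded.

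**Step 2: both limits required together.** The condition is d ≥ 25 and d ≤ 40, which is the range stated elsewhere.

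| d (mm) | As written (*or*) | Both limits jointly |
|---|---|---|
| 20 | passes | fails |
| 24.9 | passes | fails |
| 25 | passes | passes |
| 32 | passes | passes |
| 40 | passes | passes |
| 40.1 | passes | fails |
| 45 | passes | fails |

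**Step 3: the same check on a grid.** From 0 to 100 mm in steps of 0.1 mm there are 1001 values.

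- As written: 1001 admitted, 0 excluded.
- Jointly: (40.0 − 25.0)/0.1 + 1 = 151 admitted, and 1001 − 151 = 850 excluded.

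The grid only confirms the logic. It is not a distribution of patients, so 850 of 1001 says nothing about the share of candidates affected.

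**Step 4: weight of one subject.** With all 15 enrolled, one subject is 1/15 = 6.7% of the denominator, and more if fewer are enrolled. This is the leverage of a single subject, not a predicted effect.

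**Step 5: is it current text?** The *or* appears separately in the synopsis and in Section 6.5.2, so a conversion fault is unlikely. The revision history in Section 15.0 does not mention this criterion.

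**The case against.** The best reply is that the bullet should not be read alone. The stem of criterion 5 independently requires anatomy compatible with correct deployment. On the protocol's own Table 1, a 45 mm aorta is hard to call compatible. The objective in Section 4.0 concerns use within the indication, Section 6.3 ties the population to that indication, and no competing range appears anywhere. A literal reading leaves the bullet with no function, so a trained investigator (Section 12.5) is unlikely to adopt it. Exclusion 18, "Any other clinical reason, as deemed by the investigators of the study", also allows an unsuitable patient to be declined. Finally, the study is small and descriptive, and no effect on an endpoint has been shown.

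Much of this stands. The intended range can be inferred, misuse is not the likely outcome, and passing the bullet is not the same as passing all of criterion 5. That limits the severity, but it does not remove the error. The stem gives no diameter and does not refer to Table 1, and exclusion 18 is discretionary. Each safeguard works only if the reader sets aside what the operative rule says.

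Two neighbouring points carry no weight here. The bullet names the ascending aorta and arch while the indication names the filter site, but the first includes the second, so they do not conflict. The protocol promises no independent reading of the CT, so the lack of one is not an inconsistency.

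**Conclusion.** The concern holds. As written, the diameter bullet admits every diameter. It therefore conflicts with the 25 to 40 mm range in the synopsis indication, Section 3.3 and Table 1, and does not deliver the alignment claimed in Section 6.3. It is an internal inconsistency from drafting, of moderate severity, and should be fixed.

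The logic needs no assumption beyond the ordinary meaning of *or*. The practical size is unknown: the documents give no distribution of aortic diameters among candidates, so the number of out-of-range enrolments cannot be estimated, and no effect on an endpoint is claimed. Section 8.8 sets no powered success criterion, so no sample size, power or error rate is affected.

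**What to change.** Reconcile the bullet in the synopsis and in Section 6.5.2 with the range in the synopsis indication, Section 3.3 and Table 1, and state explicitly whether both limits apply jointly. If they do, a closed-range form such as the one inclusion criterion 1 already uses for age removes the ambiguity. If an open criterion is really meant, the alignment statement in Section 6.3 needs to change instead. Which limits are clinically right is for the sponsor to settle. The request is only that these passages agree.

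The cost is a change to one line in two places, made through a formal amendment with IRB approval (Section 12.9). The one downside is that some candidates whom the literal text admits might be screened out. The documents do not say how many.
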